1.0 Study Plan Overview

Objective:	To evaluate the necessity of adjunctive therapy following treatment of stenoses of a mature native arteriovenous (AV) dialysis access circuit fistula or graft with the Advance® Enforcer™ 35 Focal-Force PTA Balloon Catheter (hereafter referred to as the Enforcer balloon) compared to stenoses initially treated with commercially available conventional balloon angioplasty.
Design of the clinical study:	Multicenter, stratified, randomized, controlled clinical study
Primary endpoint:	The primary endpoint is the percentage of lesions requiring adjunctive treatment immediately following the study procedure.
Number of patients:	Approximately 200 patients (at minimum 250 lesions)
Number of clinical sites:	Up to 10 clinical sites
Patient participation duration:	Patient's medical records will be reviewed through 90 days post-procedure.
Expected study duration:	Patient enrollment is expected to be completed within 1 year of study initiation. Total study duration (from study initiation through patient enrollment and follow-up) is expected to be 15 months.

2.0 Ethical Considerations and Regulatory Compliance

This clinical study will be conducted in accordance with the study plan, the ethical principles that have their origin in the Declaration of Helsinki, and the following:

- ISO 14155^a

3.0 Objectives of the Clinical Study

The primary objective of this study is to evaluate the necessity of adjunctive therapy following treatment of stenoses of a mature native AV dialysis access circuit fistula or graft with the Enforcer balloon compared to stenoses initially treated with commercially available conventional balloon angioplasty.

4.0 Device Description

4.1 Intended Use

The Enforcer balloon is intended for percutaneous transluminal angioplasty (PTA) of lesions in peripheral arteries including iliac, renal, popliteal, infrapopliteal, femoral and iliofemoral as well as obstructive lesions of native or synthetic arteriovenous dialysis fistulae. This device is not for use in the cerebral or coronary vasculature.

For this study, the Enforcer balloon will be used in the treatment of obstructive lesions of native or synthetic arteriovenous dialysis fistula.

4.2 General Device Description

The Enforcer balloon is a double-lumen catheter with a balloon near its distal tip. Four polymer elements are incorporated into the balloon, which provide focal-force upon inflation. These elements will aid in opening lesions. Platinum/iridium, radiopaque markers are positioned on the shaft within the balloon to enable visualization of the catheter/balloon under fluoroscopy. The catheter is compatible with 0.035 inch (0.89 mm) wire guides.

^a The study will not require strict adherence to all aspects of ISO 14155: 2011. Regarding section 6.8.1, Traceability of documents and data: A signature and date from a member of the investigation team will not be necessary for all source documentation. Regarding section 6.4.1, Adverse events and section 9.8, Safety Reporting: Adverse event reporting will be limited to those events listed in this Study Plan Section 9.6: Adverse Events. Event reporting may not occur until the patient's medical record review for the 90-Day Chart Review. Regarding section 4.7.4, Information to be provided to the subject: It may not be necessary for the patient to document their agreement to inform their personal physician of participation in the study.

Please reference the device for labeling information and the manufacturer's Instructions for Use (IFU) for the following:

- Detailed description of the device
- Instructions including storage and handling requirements, preparation for use, pre-use checks, precautions to be taken after use and disposal
- Summary of the necessary training and experience required for use of these devices
- Description of the procedures involved in the use of these device

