6.3 Methods to Minimize Risks

Methods to minimize risk to patients include:

- Design of the device (as verified in nonclinical testing)
- Study design (e.g., monitoring of study conduct, limiting imaging requirements, eligibility criteria, informed consent)
- Conduct of the study at clinical sites with principal investigators qualified by training and experience
- Device will be used only by experienced investigators who have completed study training
- Study oversight by IRB
- Adverse event reporting as outlined in this study plan

- Capture, handling, and storage of the study data are done in compliance with applicable regulations to minimize the risk of release of any personal health information

The risks of the study have been minimized and the residual risks are considered acceptable because they do not outweigh the potential for benefit.

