9.6 Adverse Events

The following adverse events, occurring after the point of enrollment until the last day of patient participation, are to be reported to the sponsor using the appropriate eCRF:

- Events with potential relationship to the study device or study procedure
- Serious Adverse Events
- Restenosis or occlusion resulting in a reintervention or abandonment of AV dialysis access circuit

Information regarding occurrence of adverse events (including onset date, end date, date of awareness, event description, treatment, and whether the device or procedure contributed to the event) will be captured throughout the study and recorded on the appropriate eCRF.

Sites are responsible for following their normal reporting process (e.g., to manufacturer, to regulatory authority) for commercially available devices.

The sponsor is responsible for reporting events to the reviewing IRB(s) and principal investigator(s) as required according to applicable regulations/standards/policies.

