10.2 Early Termination or Suspension of the Clinical Study

Any decision to suspend enrollment or terminate the clinical study either completely or at multiple clinical sites will be made by the sponsor. The sponsor or the IRB may decide to suspend enrollment or terminate the study at an individual clinical site. Reasons for early termination or suspension of a study (or at one or more sites) may be due to safety concerns, effectiveness concerns, ethical concerns, alterations in accepted clinical practice, clinical site performance, or organizational issues. In the event of clinical site or study closure, all patients who have received the study treatment will be followed for 90 days following the study procedure.

The principal investigator-required notifications/reports are described in Table 10.2-1. The reports will be provided as required by the study plan, IRB policies, or local regulations, whichever is more stringent.

Table 10.2-1. Early Termination or Suspension Reports

Report	To	Timeframe to submit report (upon awareness)
IRB initiated suspension or early termination	Sponsor Patient	Within 5 working days
Sponsor initiated suspension or early termination	IRB Patient	Within 5 working days

The sponsor is responsible for reporting early termination or suspension of the study to reviewing IRB(s) and principal investigator(s) as required according to applicable regulations/standards.

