12.0 Deviations from Study Plan

Except under emergency situations when necessary to preserve the rights, safety, or well-being of study patients, principal investigators are not allowed to deviate from this study plan without documented prior approval by:

- the sponsor; and
- the IRB

Clinical study noncompliances (i.e., deviations from the study plan, investigator agreement, IRB policy, and/or any applicable regulations/standards) will be documented, along with an explanation and corrective and preventive actions, and reported to the sponsor.

The principal investigator-required notifications/reports are described in Table 12.0-1. The reports will be provided as required by the study plan, IRB policies, or local regulations, whichever is more stringent.

Table 12.0-1. Clinical Study Noncompliance Reports

Report	To	Timeframe to submit report (upon awareness)
Deviation to protect the life or physical well-being of a patient in an emergency	Sponsor IRB	As soon as possible, but no later than 5 working days
Deviation that affects the scientific soundness of the clinical study	Sponsor IRB	Within 5 working days
All clinical study noncompliances	Sponsor IRB, if required per local policy	15 working days

The sponsor is responsible for reporting clinical study noncompliances to the reviewing IRB(s) and investigator(s) as required according to applicable regulations/standards.

In accordance with applicable regulations/standards, the sponsor will review all clinical study noncompliances and take suitable action(s) to secure compliance. If appropriate, based on the number and nature of noncompliances, actions may include discontinuation of device shipment and/or termination of a principal investigator's participation in this clinical study.

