14.0 Monitoring

The conduct of the clinical study will be supervised through a process of centralized, remote, and on-site monitoring.

The sponsor will perform centralized monitoring (i.e., data review) throughout the study for adverse events, unexpected results, and for data completeness, consistency, and clarity. A formal query process in the EDC system will be utilized to resolve data discrepancies. Queries may arise from automated processes or from manual review of eCRFs, procedural reports, imaging data, or correspondence received. Principal investigators will ensure timely resolution of queries.

On-site monitoring will be implemented as necessary throughout the course of the study to ensure the principal investigators are fulfilling the obligations set forth in the study plan, agreement(s), IRB policies, and applicable regulations/standards. Source data verification will be performed during on-site visits. If allowed per site policy, some source data verification may be done remotely, according to the monitoring plan. The principal investigator and clinical site will provide direct access to source data/documents for study-related monitoring, audits, IRB review and regulatory inspection. Standard practices for monitoring the study are summarized in Appendix C.

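### Footnote a lets adverse event reports, including serious and procedural ones, wait for the 90-day chart review, and no section sets a deadline for sending them to the sponsor

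*Combined protocol and SAP*

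**What the plan says.** Footnote a lists departures from ISO 14155. On adverse events and safety reporting it makes two. The first is scope: "Adverse event reporting will be limited to those events listed in this Study Plan Section 9.6: Adverse Events". The second is timing: "Event reporting may not occur until the patient's medical record review for the 90-Day Chart Review".

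The Section 9.6 list includes "Serious Adverse Events" and "Events with potential relationship to the study device or study procedure", so the timing departure covers both groups. Section 9.6 sets no reporting time. Table 15.2-1, which lists the investigator's reports, has no adverse event row and no time column. Section 10.0 has information on patients who leave the study, death included, reach the sponsor during the 90-day chart review.

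Other sections assume that the sponsor has events in hand while the study runs:

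- Section 6.3 counts this among its methods to minimize risk: "Adverse event reporting as outlined in this study plan".
- Section 14.0: "The sponsor will perform centralized monitoring (i.e., data review) throughout the study for adverse events".
- Section 10.2: "Reasons for early termination or suspension of a study (or at one or more sites) may be due to safety concerns".
- Section 9.6 makes the sponsor responsible for passing events on to the IRBs and principal investigators.

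Deadlines do exist for other reports. In Table 12.0-1 an emergency deviation to protect a patient is due "As soon as possible, but no later than 5 working days", a deviation affecting scientific soundness within 5 working days, and any noncompliance within 15. Table 10.2-1 gives 5 working days for reports of suspension or early termination.

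**The concern.** Centralized review and discretionary suspension can act only on what the sponsor has received. A site could leave a serious or procedural event unentered until day 90 and still point to footnote a, while a minor noncompliance must be reported within 15 working days.

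The delay has least justification for procedural harms. Section 7.5.2 names rupture and circumferential tears as safety measures. Appendix D defines rupture by extravasation of contrast, and Section 9.3 calls for completion angiography straight after the study balloon. The operator will therefore normally know of a rupture on the day, and a chart review three months later adds nothing to that knowledge.

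At stake is how many further patients may be treated before the sponsor must hear of such an event. The primary endpoint and its analysis are not affected.

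**Working it through.** **Inputs from the plan**

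- Enrollment: about 200 patients, at least 250 lesions (Sections 1.0, 7.1, 11.1).
- Enrollment period: 1 year; total duration 15 months (Section 7.3).
- Permitted reporting point: the 90-day chart review (footnote a).
- Share of patients with a second treated lesion: 40% (Section 11.1).
- Allocation: 1:1 (Sections 7.4.1, 11.2).

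**Assumption:** uniform accrual. The plan gives no accrual curve.

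**Step 1. Reproduce the plan's timeline.** 12 months of enrollment + 90 days (about 3 months) = 15 months, as stated.

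**Step 2. Patients treated during one permitted delay.** For an event on the day of the procedure, with the chart review held at day 90:

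- Patients = N × 90 / 365.
- N = 200: 200 × 90 / 365 = 49.3, or 90 / 365 = 25% of the trial.
- Per arm: 100 × 90 / 365 = 24.7, about 25.
- Lesions: 250 × 90 / 365 = 61.6, about 62.

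**Step 3. Fewer patients.** If 40% have a second lesion, 250 lesions need 250 / 1.4 = 179 patients, and 178.6 × 90 / 365 = 44.

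**Step 4. Sensitivity to the length of accrual (assumed values).**

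| Accrual period | 179 patients | 200 patients |
|---|---|---|
| 9 months (274 days) | 59 | 66 |
| 12 months (365 days) | 44 | 49 |
| 18 months (548 days) | 29 | 33 |

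**Step 5. Events later in follow-up.** An event on day d may wait 90 − d days. At d = 60 that is 30 days, and 200 × 30 / 365 = 16 patients. The figure of 49 therefore applies to procedural events. The plan gives no window for the chart review, so a review held after day 90 would lengthen each of these delays.

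**Step 6. Compare the texts on timing.**

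| Place | What it implies | Time limit for adverse events |
|---|---|---|
| Footnote a | Reporting may wait for the 90-day review | None before that review |
| Section 9.6 | Events recorded over the whole course of the study | None |
| Section 13.0 | Data to be supplied promptly | None |
| Section 14.0 | Sponsor reviews events, procedural reports and images during the study | None |
| Appendix B | Adverse events marked at the procedure and at 90 days | None |
| Appendix C, 2.2 | Monitors check charts and timeliness of reports as needed | None |

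The footnote is the only text that speaks directly to when an event report may arrive, and it points the opposite way from the rest.

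**The case against.** The best defence is that the footnote should not be read alone. Section 13.0 imposes a general duty of prompt submission, Section 9.6 has events recorded as the study proceeds, and Appendix B marks adverse events on the procedure day. Angiographic images go to the sponsor under Section 9.3, and Section 14.0 covers imaging and procedural reports, so a rupture may become visible that way. Appendix C has monitors review charts. Sites keep their usual reporting to manufacturers and regulators, and must meet their IRB's requirements. The Enforcer balloon is FDA cleared, AV dialysis fistula lesions are within its intended use, and the comparator is commercially available. On this view the footnote merely describes when events come to light in a study followed by chart review.

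Much of this stands. It rules out two stronger readings:

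- A reader might infer that sites are told to hold every report, or that events in patients enrolled during the last 90 days of accrual can play no part in a suspension decision. The documents do not support that. The footnote permits delay and does not forbid earlier reporting, and several earlier routes exist.
- A reader might infer that a cluster of ruptures would probably go unseen. The plan gives no rupture rate. Its nearest figure, 1 of 28 patients (3.6%) in the earlier single-arm study (Section 5.0), concerns access site complications. The plan also has no numeric safety stopping rule. No expected count of unseen events can be drawn from it.

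What does not stand is the claim that these provisions settle the matter. None carries a time limit and none overrides the footnote. Monitoring visits occur as needed, and reports to manufacturers or regulators are not routed into the study database.

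**Conclusion.** The point holds in this form: footnote a allows all Section 9.6 events, serious and procedural ones included, to wait for the 90-day chart review; no passage sets a deadline for sending them to the sponsor; and this conflicts with the sections that expect or depend on earlier receipt. Under uniform accrual over 1 year with the review at day 90, up to about 49 of 200 patients (44 of 179), about 25 per arm in a trial of 200, could be treated before a procedural event must reach the sponsor. That is the most the plan allows under these assumptions, not a forecast of the actual lag. It rises or falls with the accrual rate and shrinks for events later in follow-up. The consequence falls on discretionary safety oversight. It is a worthwhile and inexpensive improvement to the plan.

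**What to change.** Reconcile footnote a with Sections 9.6, 10.0, 13.0 and 14.0 and Appendix B:

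1. In footnote a, limit the delay to events that do not meet the serious definition and are first found at chart review. Other non-serious events already known to the site then fall under the general duty in Section 13.0.
2. In Section 9.6, and as a row with its time limit in Table 15.2-1, require deaths, serious adverse events, vessel rupture and circumferential tear known to the site to be entered in the EDC within 5 working days of awareness. Table 12.0-1 already uses that time frame.
3. State that a reintervention meeting the serious definition in Appendix D belongs to the 5-day group, although restenosis or occlusion leading to reintervention is listed separately in Section 9.6.
4. Define circumferential tear in Appendix D, which defines rupture and dissection but not tear.

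The cost is a few sentences, one table row, one definition and earlier entry of a small number of events. No extra visits or patients are needed, and the analysis is unchanged. The date of awareness is already among the event data in Section 9.6, so compliance can be checked. One limit remains: a clock that starts at awareness does nothing for events after discharge that the site first learns of at chart review.

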4.3 Device Identification and Tracking

The study device is FDA cleared for use in the United States and will be obtained through standard commercial processes. Information regarding device dimensions and lot numbers will be reported through an electronic data capture system.

5.0 Background Information

The safety and performance of the Enforcer balloon were assessed through a series of nonclinical tests performed in accordance with verified methods and procedures to maintain the integrity of the results. The testing results provide reasonable assurance that the potential risks associated with the use of the device have been mitigated to an acceptable level. Additionally, conventional balloon angioplasty is a standard treatment for dialysis access dysfunction and several clinical evaluations have been performed and reported in literature, which assess safety and performance of angioplasty using different balloon technologies (e.g., conventional balloons, high pressure balloons, cutting balloons).¹

A prospective, single-arm, single-center clinical evaluation of the Enforcer balloon was previously conducted to evaluate the treatment of AV access stenoses.² The study evaluated the treatment of 39 AV fistula lesions in 28 patients who were treated with 37 Enforcer balloons; patients were followed for 6 months post-procedure. Device success, defined as < 30% residual stenosis immediately following treatment was 64.1% (25/39). Similarly, 92.3% (36/39) of lesions were reduced to < 50% residual stenosis. Overall, treatment with the Enforcer balloon led to a reduction in the average percent diameter stenosis of the treated lesion from 66.3% pre-procedure to 23.7% post-procedure. The average maximum inflation pressure required was 12.3 atm. Only one lesion required adjunctive treatment following angioplasty with the study balloon, indicating that

clinically relevant luminal gains can be achieved with the study device alone, without the need for a high pressure balloon or other additional therapies.

Following the study procedure, all patients could resume normal dialysis. The Kaplan-Meier estimates for patency at 90 days and 6 months were 62.0% and 25.1%, respectively. The rate of access site complications were low (1/28; 3.6%). Overall, the data supported the safety of the Enforcer balloon for the treatment of stenotic lesions in mature native AV hemodialysis access circuits.

6.0 Risk Analysis and Risk Assessment

6.1 Risks and Foreseeable Adverse Events

Please reference the IFU for the following:

- Potential adverse events
- Warnings
- Precautions

In addition, participation in this clinical study is associated with the following risk:

- Release of personal information

6.2 Anticipated Clinical Benefits

Percutaneous transluminal angioplasty of a stenosed lesion in an AV access circuit could result in a resumption of normal hemodialysis.

6.3 Methods to Minimize Risks

Methods to minimize risk to patients include:

- Design of the device (as verified in nonclinical testing)
- Study design (e.g., monitoring of study conduct, limiting imaging requirements, eligibility criteria, informed consent)
- Conduct of the study at clinical sites with principal investigators qualified by training and experience
- Device will be used only by experienced investigators who have completed study training
- Study oversight by IRB
- Adverse event reporting as outlined in this study plan

- Capture, handling, and storage of the study data are done in compliance with applicable regulations to minimize the risk of release of any personal health information

The risks of the study have been minimized and the residual risks are considered acceptable because they do not outweigh the potential for benefit.

7.0 Design of the Clinical Study

7.1 Design of the Clinical Study

This multicenter, stratified, randomized, controlled clinical study will evaluate the performance of the Enforcer balloon compared to commercially available conventional balloons (defined as less than 25 atm rated burst pressure) in the treatment of stenoses of the AV dialysis access circuit.

This study will enroll approximately 200 patients at up to 10 clinical sites. Enrollment will end when it is determined a minimum of 250 lesions have been treated.

7.2 Study Design Rationale

A randomized clinical trial allows for the direct comparison of the rates of adjunctive treatment between the Enforcer balloon and other commercially available standard angioplasty balloons.

